## **9. STATISTICAL METHODOLOGY AND STATISTICAL ANALYSES**

Statistical analysis and data presentation will be performed on the subgroups of patients aged 6 years to less than 18 years, and patients aged 18 years to less than 21 years, respectively. A pooled data analysis including all the patients enrolled in the study will also be performed. Also, analysis of time-to-event efficacy endpoints will be performed only if sufficient number of events permit meaningful estimates.

### **9.1. Statistical METHODS AND ANALYSES**

#### **9.1.1. Analysis of Primary Endpoint**

Descriptive statistics for observed and dose-corrected (where appropriate) PK data will be reported for all patients with at least one PK observation by presenting the population size, arithmetic mean, standard deviation, percent coefficient of variation (CV%), median, minimum, maximum values. In addition, geometric mean and the 95% CI for the geometric mean will be reported where appropriate.

The key PK parameters in pediatric patients will be compared to adult patients with GIST based on historical data. The formal comparison will be carried out as part of the NONMEM portion using the historical PK data in adult GIST patients.

#### **9.1.2. Analysis of Efficacy Endpoints**

##### **9.1.2.1. Objective Response Rate**

Objective response rate (ORR) is defined as the proportion of patients with a confirmed complete (CR) or partial response (PR) relative to the number of patients in the treatment group according to RECIST criteria (Version 1.1). The number and percent of patients achieving objective response (CR or PR) will be summarized along with the corresponding exact 2-sided 95% CI calculated using a method based on the F distribution.

##### **9.1.2.2. Progression-Free Survival**

Progression-free survival (PFS) is defined as the time from the date of enrollment to the date of the first documentation of objective tumor progression or death due to any cause, whichever occurs first. PFS data will be censored on the day following the date of the last

---

## Protocol A6181196 Statistical Analysis Plan - Version 1.0 Final

---

tumor assessment documenting absence of progressive disease for patients who 1) are given anti-tumor treatment other than the study treatment prior to observing objective tumor progression; 2) are removed from the study prior to documentation of objective tumor progression; 3) are ongoing at the time of the analysis.

Patients who do not have any post-baseline tumor assessments will have their PFS endpoint censored on the date of enrollment. Death or disease progression that occurs after more than one missed visit will be censored on the day following the date of the last tumor assessment as well.

PFS will be summarized using Kaplan-Meier methods and displayed graphically where appropriate. Median PFS and its corresponding 2-sided 95% CI for the median will be provided.

### **9.1.2.3. Duration of Response**

Duration of response (DR) is defined as the time from the first objective documentation of complete or partial response that is subsequently confirmed to the first documentation of disease progression or to death due to any cause, whichever occurs first. DR will be calculated for the subgroup of patients with objective disease response. DR will be summarized using Kaplan-Meier methods and displayed graphically where appropriate. The median event time and 2-sided 95% CI for the median will be provided if appropriate. The number of patients experiencing CR and PR may be small and thereby limit the use of the Kaplan-Meier method to provide reliable information. In this case, descriptive statistics or listings will be provided.

### **9.1.2.4. Overall Survival**

Overall survival (OS) is defined as the time from enrollment to the date of death due to any cause. OS data will be censored on the day following the date of the last contact at which the patient is known to be alive. OS will be summarized using Kaplan-Meier methods and displayed graphically where appropriate. The median survival time and 2-sided 95% CI for the median will be estimated.

The 2-year survival probability will be estimated using the Kaplan-Meier method and a 2-sided 95% CI will be constructed for the 2-year survival probability.

### **9.1.3. Analysis of Safety Endpoints**

The per protocol population will be the analysis population for evaluating safety endpoints.

#### **9.1.3.1. Analysis of Adverse Events**

All AEs reported during the AE reporting period will be considered as treatment-emergent AEs, unless present at baseline with the same severity grade. All AEs will be coded by system organ class (SOC) and preferred term using MedDRA. The severity of all AEs will be coded by the investigator using NCI CTCAE Version 4.0.

---

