**17. Echocardiogram or MUGA scan** at screening, then on Day 1 of every 3rd cycle (for example, Day 1 Cycle 3, Day 1 Cycle 6 ..etc.). As clinically indicated at the end of treatment/withdrawal per [Section 6.3.1](#) and see suggested dose modifications guidelines for left ventricular systolic dysfunction in [Section 5.2.10](#).

18. Adverse Events: Patients must be followed for adverse events from the first day of study treatment until 28 days after the last dose of study treatment, or until all serious or study drug-related toxicities have resolved or are determined to be “chronic” or “stable,” whichever is later. Serious adverse events should be monitored and reported from the time that the patient provides informed consent as described in the protocol.

19. Study Drug Compliance: Unused sunitinib will be returned to clinic for drug accountability at the beginning of each subsequent cycle.

20. Concomitant Medications/Treatments will be recorded from 28 days prior to the start of study treatment, during the study and up to 28 days after the last dose of sunitinib.

21. Follow-up Survival Monitoring: Follow-up survival information, including post-study anti-cancer treatment, will be collected by clinic visit or telephone contact every 3 months until death, or either 24 months from patient’s first dose of study treatment or completion of 18 cycles. See Section 6.3.2.

22. Growth and Pubertal Maturation Assessments (for pediatric patients only): Bone age assessments must be performed at screening, and then annually with an additional test at End of Treatment or until growth plate closure. Tanner staging must be performed at screening. If patient is Tanner Stage 1-4, then Tanner assessment should be repeated every 6-9 months and at End of Treatment or until patient reaches Tanner Stage 5. Refer to Section 7.3 Growth and Pubertal Maturation Assessments. Tanner staging assessments can only be waived upon agreement by Pfizer. If Tanner staging is initiated it should be continued per Section 7.3.

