- Hematology and Chemistry: See [Section 7.2.2](#) for specific tests;
- Thyroid stimulating hormone (TSH);
- Urinalysis (dipstick test). (If the results of the dipstick test indicate a  $\geq 2+$  proteinuria, then follow-up should be performed with a quantitative urine protein analysis according to local standard practices);
- Prothrombin time or INR (The same test should be used throughout the study);
- Pregnancy test (urine), if applicable, within 7 days before initiation of study therapy (refer to [Section 7.2.3](#));
- Three 12-lead ECGs approximately 2 minutes apart, preferably in the morning;
- ECHO or MUGA scan;
- MRI (or CT) scan of abdomen and pelvis, in addition to any other applicable sites of disease;
- Chest radiograph if tumor imaging (with MRI or CT scan) does not include the chest;
- Bone age determination for patients < 18yrs;
- FDG-PET, if locally available;
- Assessment of concomitant medications and treatments;
- Assessment of ongoing symptoms/events (serious adverse events must be recorded from time of signed consent);
- Study registration.

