## 7.2. Safety Assessments

### 7.2.1. Adverse Events

Assessment of adverse events will include type, incidence, severity (graded by the NCI CTCAE v4.0), timing, seriousness, and relatedness; and laboratory abnormalities.

Baseline tumor-related signs and symptoms will be recorded as adverse events during the trial if they worsen in severity or increase in frequency.

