#### **8.2. Reporting Period**

For serious adverse events, the active reporting period to Pfizer or its designated representative begins from the time that the patient provides informed consent, which is obtained prior to the patient's participation in the study (ie, prior to undergoing any study-related procedure and/or receiving investigational product) through and including 28 calendar days after the last administration of the investigational product.

SAEs occurring to a patient after the active collection period has ended should be reported to the sponsor if the investigator becomes aware of them; at a minimum, all SAEs that the investigator believes have at least a reasonable possibility of being related to investigational product are reported to the sponsor.

- Adverse events (serious and non-serious) should be recorded on the CRF from the time the patient has taken at least one dose of study treatment through the patient's last visit.
- If a patient begins a new anticancer therapy, the adverse event reporting period for non-serious adverse events ends at the time the new treatment is started. Death must be reported if it occurs during the serious adverse event reporting period after the last dose of investigational product, irrespective of any intervening treatment.

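### The treatment-emergent rule in SAP 9.1.3.1 drops only events at exactly the baseline grade and has no first-dose anchor, so it can misclassify improved conditions, more frequent tumor symptoms and possibly pre-dose SAEs

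*SAP*

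**What the plan says.** SAP 9.1.3.1 gives the only definition of treatment-emergent in either document: "All AEs reported during the AE reporting period will be considered as treatment-emergent AEs, unless present at baseline with the same severity grade". It does not define the AE reporting period or the AE baseline. SAP 9.1.3.2 defines a baseline, but for laboratory data. Protocol 9.5.1 restricts the AE analysis to treatment-emergent events without defining the term.

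The protocol describes the start of AE reporting in two ways.

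- **From consent, for SAEs.** Section 8.2: "For serious adverse events, the active reporting period to Pfizer or its designated representative begins from the time that the patient provides informed consent". Schedule of Activities, footnote 18: "Serious adverse events should be monitored and reported from the time that the patient provides informed consent as described in the protocol". Section 6.1: "serious adverse events must be recorded from time of signed consent".
- **From first dose, for AEs.** Section 8.2 says of AEs, serious and non-serious alike, that they "should be recorded on the CRF from the time the patient has taken at least one dose of study treatment". Schedule of Activities, footnote 18: "Patients must be followed for adverse events from the first day of study treatment until 28 days after the last dose of study treatment".

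Protocol 7.2.1 sets a separate recording rule for tumor-related signs and symptoms present at baseline: they "will be recorded as adverse events during the trial if they worsen in severity or increase in frequency". The documents state no such limit for other baseline conditions.

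**The concern.** A treatment-emergent definition should pick out what is new or worse after the first dose. This one tests only whether the grade equals the baseline grade, and it does not mention the first dose. Three kinds of event can therefore be put in the wrong class:

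- a condition that improved on treatment;
- a tumor symptom that became more frequent without changing grade;
- a serious event that occurred in screening before any drug was given.

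The first and third would add to the AE tables, and the second would take away from them. AEs are a secondary endpoint, and SAP section 9 calls for separate analysis of patients aged 6 to under 18. Protocol 9.1 now puts that group at 6 patients, so a single patient is visible in any rate.

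**Working it through.** The plan states no figure for this rule, so the check works through the rule itself.

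**1. Grade pairs.** Take baseline grade b = 0 (absent) to 4 and on-treatment AE grade p = 1 to 5, which gives 5 × 5 = 25 pairs.

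- SAP rule: emergent unless b = p. Four pairs are removed (1→1, 2→2, 3→3, 4→4), so 25 − 4 = 21 are emergent.
- New-or-worsened rule: emergent if p > b, which gives 5 + 4 + 3 + 2 + 1 = 15.
- Difference: 21 − 15 = 6 pairs (2→1, 3→1, 3→2, 4→1, 4→2, 4→3), all of them improvements.

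These are counts of possible pairs, not expected frequencies.

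**2. Can an improved condition be reported as an AE?** Improved tumor-related symptoms cannot, because protocol 7.2.1 keeps them out at recording. Other conditions can. Schedule of Activities footnote 6 makes any abnormal examination finding after screening an AE, with no requirement that it be worse than before. Section 8.3 gives changed examination findings as an example of an AE.

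**3. More frequent tumor symptoms.** Suppose a Grade 2 symptom is present before dosing and occurs more often, still at Grade 2, on treatment. Section 7.2.1 records it as an AE. The SAP rule sees b = p = 2 and removes it. This result does not depend on how the reporting period is read.

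**4. Pre-dose SAEs under each possible window.**

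| Status at baseline | Window opens at consent | Window opens at first dose (CRF) |
|---|---|---|
| Resolved | counted | not counted |
| Ongoing, lower grade at baseline | counted | not counted |
| Ongoing, same grade | not counted | not counted |

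Restricting safety analysis to treated patients (SAP 5.2) does not settle this, because it selects patients and not onset dates.

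**5. Scale of one misclassified patient.**

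- 6 children (protocol 9.1): 1/6 = 16.7 percentage points.
- 21 pooled, assuming all 15 young adults allowed by protocol section 3 are enrolled (6 + 15): 1/21 = 4.8 points.

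**The case against.** The best defense is that the cases are rare and the output makes them visible. Section 7.2.1 already keeps out improved tumor symptoms. Inclusion criterion 7 requires acute toxicities of earlier treatment to be Grade 1 or lower at entry, and an improvement from Grade 1 leaves nothing to grade. What remains is a condition that is not tumor-related, is not acute prior-treatment toxicity, is Grade 2 or more at baseline, improves, and is still reported. The SAP also summarizes treatment-related events by investigator attribution and lists all AE data by patient. Reporting is descriptive, so no test depends on these counts. All of this stands as a limit on frequency and consequence. None of it corrects the sentence.

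It can also be said that section 7.2.1 governs recording and the SAP rule governs classification, so they run in sequence and cannot conflict. That is right for improved tumor symptoms. It fails for a symptom that becomes more frequent at the same grade, which the first rule lets in and the second removes.

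A reader might infer that pre-dose SAEs will be counted as treatment-emergent. The documents do not support that as a certainty. Section 8.2 starts CRF recording of serious and non-serious events at first dose, and the SAP takes relatedness and AE discontinuations from the CRF. On that reading no pre-dose SAE reaches the tables. On the consent reading, one ongoing at baseline at the same grade is still removed. Because section 6.1 requires SAEs to be recorded from consent and the SAP names no window, the point is an unresolved ambiguity.

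**Conclusion.** The point holds as a minor defect of definition. Two misclassifications follow from the text alone: an AE reported below its baseline grade is counted, and a tumor symptom that is more frequent at an unchanged grade is dropped. The third, a counted pre-dose SAE, is conditional on the consent-based window and on the event being resolved or at a different grade at baseline.

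The number of patients affected cannot be derived from the documents and is probably small. The per-patient shifts of 16.7 and 4.8 points are the weight of one patient, not estimates of bias. The exposure lies mainly in the all-causality AE and SAE tables, since investigator attribution partly protects the treatment-related ones.

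Two stronger readings should be avoided. Protocol 2.2 lists AEs first among the secondary endpoints but does not rank them as the main one. Nor does the rule by itself attribute events to sunitinib, because treatment-emergence is a matter of timing and change, while causality is assessed separately.

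**What to change.** Replace the SAP sentence with a definition along these lines:

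*A treatment-emergent AE either has its onset on or after the first dose and within the AE reporting period set by the protocol, or was present before the first dose and afterwards worsens in CTCAE grade or, for baseline tumor-related symptoms, becomes more frequent. Otherwise, an event at the same or a lower grade than baseline is not treatment-emergent.*

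In addition:

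- Define the AE baseline as the last status before the first dose.
- List pre-dose SAEs separately.
- Reconcile the start of AE reporting across protocol 8.2, protocol 6.1 and Schedule of Activities footnote 18.
- Reconcile its end as well. Section 8.2 closes active SAE reporting 28 days after the last dose but continues CRF recording to the last visit. Footnote 18 extends follow-up past 28 days until serious or drug-related toxicities have resolved or stabilized.
- Do not settle the end by writing a new 28-day onset limit into the SAP. That could drop later events the protocol still collects. Any later-onset event left outside the agreed window should still be listed.

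The cost is a short SAP revision, minor programming, a protocol clarification and slightly different all-causality counts. No new data are needed.

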## Protocol A6181196 Statistical Analysis Plan - Version 1.0 Final

---

An overall summary of AEs will be provided. The number and percentage of patients who experienced any AE, who experienced any serious adverse event (SAE), who experienced any treatment-related AE, who experienced any treatment-related SAE, and who discontinued because of an AE will be presented. Treatment-related AEs are those judged by the investigator to be at least possibly related to the study drug (with a cause related to the study drug indicated on the CRF).

All AEs will be summarized by MedDRA SOC and preferred term. A summary of AEs by preferred term and maximum CTCAE grade will also be presented.

Treatment-related AEs will be summarized by MedDRA SOC and preferred term. A summary of treatment-related AEs by preferred term and maximum CTCAE grade will also be presented.

Deaths will be summarized by time period (on-study vs. during follow-up) and cause of death. Deaths that occurred within 28 days after the last dose of study medication are defined as on-study deaths. Death data will also be listed.

Patients who withdraw from study treatment because of an AE will be listed. Patient discontinuation will be determined from the end of study (EOS) evaluation (where reason for termination is “Adverse Event”) and the specific AE(s) will be determined from the AE CRF page (where action taken is “Permanently Discontinued”).

SAEs and treatment-related SAEs will be summarized by MedDRA SOC and preferred term. Patients who experienced a SAE will be listed.

Individual patient listings will be prepared for all AE data.

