### **6.4. Patient Withdrawal / End of Treatment**

End of study occurs when the patient has completed 18 cycles of therapy, has completed follow-up survival, was lost to follow-up, or in the event of the patient's unplanned death.

Patients may withdraw from the study at any time at their own request, or they may be withdrawn at any time at the discretion of the investigator or sponsor for safety or behavioral reasons, or the inability of the subject to comply with the protocol required schedule of study visits or procedures at a given study site.

If a patient does not return for a scheduled visit, every effort should be made to contact the subject. In the case of a patient lost to follow-up the appropriate box should be checked off in the Patient Summary-End of Treatment CRF page. In any circumstance, every effort should be made to document patient outcome, if possible. The investigator should inquire about the reason for withdrawal, request the patient to return all unused investigational product, request the patient to return for a final visit, if applicable, and follow-up with the patient regarding any unresolved adverse events (AEs).

If the patient withdraws from the study, and also withdraws consent for disclosure of future information, no further evaluations should be performed, and no additional data should be collected. The sponsor may retain and continue to use any data collected before such withdrawal of consent.

In addition, patients may be withdrawn from treatment in the case of:

- Disease progression, unless there is reasonable evidence of clinical benefit to justify continuation on protocol (the latter must be discussed with the Sponsor);
- Unacceptable toxicity;
- Need for treatment rest >4 weeks (if investigator considers there is potential for sustained clinical benefit, this may be discussed with the Sponsor);
- Need for anticancer therapy not specified in the protocol;
- Patient noncompliance;
- Patient lost to follow-up;
- Patient choice to withdraw from treatment (follow-up permitted by patient);
- Withdrawal of patient consent (cessation of follow-up);
- Completion of study therapy (18 cycles of study treatment; or maximum 24 months).

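### SAP 9.1.3.1 finds patients who stop treatment for an adverse event through their end-of-study reason, which read literally can omit a patient who stops for toxicity and stays in survival follow-up

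*SAP*

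**What the plan says.** SAP 9.1.3.1 makes two commitments. The overall AE summary will give the number and percentage of patients "who discontinued because of an AE will be presented". For the listing, "Patients who withdraw from study treatment because of an AE will be listed".

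The rule that follows has two parts. To find the patient: "Patient discontinuation will be determined from the end of study (EOS) evaluation", where the reason for termination is Adverse Event. To name the event: "the specific AE(s) will be determined from the AE CRF page", where the action taken is Permanently Discontinued.

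Protocol 6.4 defines the end of study this way: "End of study occurs when the patient has completed 18 cycles of therapy, has completed follow-up survival, was lost to follow-up"; the sentence adds death as the remaining case. It deals with stopping treatment separately: "In addition, patients may be withdrawn from treatment in the case of", followed by a list that includes "Unacceptable toxicity". The same section also mentions an end-of-treatment form. For a patient lost to follow-up, the "appropriate box should be checked off in the Patient Summary-End of Treatment CRF page".

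**The concern.** The listing concerns stopping the drug, but the patient is found by the reason for leaving the study. Where those are different events on different dates, the second is a poor source for the first. The AE page, which does record that the drug was stopped, comes into the rule only after the patient has been found.

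What is at stake is the AE-discontinuation listing and, on the natural reading, the matching summary count. Both bear on two secondary objectives in Protocol 2.1: safety and tolerability in general, and whether children tolerate doses above the established pediatric MTD. For a patient of the kind described, the error can only lower the count. With so few children, a reported zero could be misread as good tolerability.

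**Working it through.** The plan states no figure for AE discontinuations, so there is none to reproduce. The check applies the SAP rule to the protocol's own definitions and then sizes the effect.

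**Step 1. Follow one patient through the rule.** Suppose a patient stops sunitinib for toxicity and agrees to further contact.
- Protocol 6.4 allows withdrawal from treatment for toxicity, and separates a patient who stops treatment but permits follow-up from one who withdraws consent.
- Protocol 6.3.2 continues survival contacts every 3 months until death, 2 years from first dose, or completion of 18 cycles. A patient who stopped early will not complete 18 cycles, so follow-up runs to death or 2 years unless contact is lost.
- The end-of-study reason is then completed follow-up, loss to follow-up or death. If the patient is still in follow-up at the analysis, there is no end-of-study reason yet.
- In none of these cases is the reason Adverse Event, so the rule as written does not select the patient.

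**Step 2. Find who is still counted.** Protocol 6.4 also lets the investigator or sponsor withdraw a patient from the study for safety. Several toxicity rules are worded at study or trial level: 5.2.8 (long interruption, to be considered), 5.2.10 (higher-grade systolic dysfunction) and 5.2.11 (Grade 4 or persistent hypertension). Such patients could properly have Adverse Event as their end-of-study reason. Other rules, in 5.2.9 and part of 5.2.10, take the patient off protocol therapy only. Whether a patient is counted may therefore turn on which wording applied.

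**Step 3. Size.** The inputs are 6 children and up to 15 young adults (Protocol 3), so at most 6 + 15 = 21 pooled; SAP 9 calls for both subgroup and pooled analyses. The number of missed patients is an assumption, and all enrolled patients are taken as treated. The rate is x/n with an exact (Clopper-Pearson) 95% CI; for x = 0 the upper limit is 1 − 0.025^(1/n).

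| Group | Missed patients | Reported by the literal rule | True rate |
|---|---|---|---|
| Children, n = 6 | 1 | 0/6 = 0% (0 to 45.9%) | 1/6 = 16.7% (0.4 to 64.1%) |
| Children, n = 6 | 2 | 0/6 = 0% (0 to 45.9%) | 2/6 = 33.3% (4.3 to 77.7%) |
| Pooled, n = 21 | 1 | 0/21 = 0% (0 to 16.1%) | 1/21 = 4.8% (0.1 to 23.8%) |
| Pooled, n = 21 | 2 | 0/21 = 0% (0 to 16.1%) | 2/21 = 9.5% (1.2 to 30.4%) |

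**Step 4. Could it arise?** The documents give no expected rate of AE discontinuation. For an assumed true rate p, the chance of at least one among 6 children is 1 − (1 − p)^6:
- p = 10%: 1 − 0.9^6 = 47%
- p = 20%: 1 − 0.8^6 = 74%
- p = 30%: 1 − 0.7^6 = 88%

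These are chances that a discontinuation occurs, not that the rule misses it. A miss also requires that the patient stays in the study and that the form is completed later.

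**The case against.** The strongest reply is that the undercount depends on a form that cannot be seen. It arises only if the end-of-study evaluation is completed after survival follow-up. The Schedule of Activities has End of Treatment and Follow-up columns but no end-of-study visit. The SAP pairs the form with a drug action, which fits a form filled in when dosing stops. The protocol also blurs the two terms. Section 6.4 carries end of treatment in its heading but opens by defining end of study. It records loss to follow-up, itself an end-of-study event, on the end-of-treatment page. Footnote 4 of the Schedule times end-of-treatment assessments to study withdrawal. This stands: the documents do not settle which form is meant. It does not clear the rule, because a programmer who follows the text has no assurance of using the right page.

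A second reply is that the information survives elsewhere. Protocol 8.11 requires withdrawal due to an AE to be told apart from other causes and recorded on the AE page, and both documents promise individual listings of all AE data. This also stands. The events can be recovered; the dedicated listing and the headline count are what would be wrong.

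Third, the rule is written beside the listing, and the SAP does not state that the summary count uses it. That is the natural reading only.

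**Conclusion.** The target and the source do not match in SAP 9.1.3.1. Read literally against Protocol 6.3.2 and 6.4, the rule omits a patient who stops for toxicity and stays in survival follow-up. Each such patient lowers the reported rate by 16.7 percentage points among 6 children, or 4.8 points among 21 pooled.

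This rests on three assumptions: the form is completed at the end of study and not when treatment stops; the affected patient is withdrawn from treatment only; and the summary count follows the listing rule.

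A reader might infer that every AE discontinuer will be lost, or that the count is driven to zero. The documents do not support that. The case report forms are not available, patients withdrawn from the study for safety are counted, and the number missed is hypothetical. The primary PK endpoint does not depend on this rule. Severity is moderate to low: worth correcting before programming, but no threat to the trial's main result.

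**What to change.** In SAP 9.1.3.1, define an AE discontinuation of treatment as either an AE record with action taken Permanently Discontinued, or an end-of-treatment page giving an adverse event as the reason, if that page records reasons. Reconcile the two sources and resolve differences before database lock. State that the same definition serves both the listing and the summary count. Report end-of-study reasons separately in the disposition table.

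Using the AE action to identify patients makes the count right whichever form the SAP meant. The cost is a sentence or two in the SAP and a small amount of programming and reconciliation. The SAP already relies on the AE action field, so no new data collection is expected for that part. The documents mention the end-of-treatment page only for loss to follow-up, so whether it holds a reason field must be checked. No clinical rule changes.
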